**Table 1. Concomitant Treatments that are prohibited**

Use category	Type of medication	Details
	Adenovirus vaccine, live; BCG live intravesical; Influenza nasal vaccine, live; Measles/Mumps/Rubella vaccine, live; Rotavirus vaccine, live; Smallpox vaccine (live vaccinia virus); Typhoid vaccine, live; Varicella vaccine, live; Yellow fever vaccine, live; Zoster vaccine, live	Prohibited 2-weeks prior to randomization and for 3 months after completing the study.
Permitted with restrictions*	Strong inducers (e.g., rifampin, rifabutin) and strong inhibitors (e.g., itraconazole, erythromycin, telithromycin, clarithromycin) of CYP3A4 and P-gp	Prohibited 2-weeks prior to randomization and throughout the study.
Permitted with restrictions*	Benzodiazepines (stable dose)	Benzodiazepines are permitted only if the patient has been taking a stable regimen and dose at least 4 weeks prior to randomization. The dosage prior to randomization should be no more than Clonazepam maximum dose 3 mg/day or equivalent. For patients reporting significant treatment-emergent nervousness, restlessness, and/or akathisia, study clinicians are allowed to increase the dose of the concomitant benzodiazepine anxiolytic up to additional clonazepam 1 mg/day equivalents.
	Modulators of CYP3A4 and P-gp; drugs that could increase sirolimus blood concentrations (e.g., bromocriptine, cimetidine, cisapride, clotrizamole, danzol, diltiazem, fluconazole, protease inhibitors, metoclopramide, nicardipine, troleandomycin, verapamil); drugs and other agents that could decrease sirolimus levels (e.g., carbamazepine, phenobarbital, phenytoin, rifapentine, St. John's Wort); drugs with concentrations that could increase when given sirolimus (e.g., verapamil).	Permitted only at the discretion of the prescriber after careful review of concomitant medications.

**Notes:** Sedatives, hypnotics, benzodiazepines, sedating antihistamines or other psychotropic medications are not permitted within 8 hours of treatment sessions; except – at the discretion of the investigator – for medications that will results in discontinuation/withdrawal symptoms or that may alter the risk benefit ratio.

\*All prescribers will be provided with the list of prohibited and restricted medications as detailed in the sirolimus manufacturer information and made aware that medications should be used with caution.

***Privacy:***

All reports generated from the data obtained through this study will protect the confidentiality of the subjects who participate in this study. In case of a medical emergency, the medication group blinding can be broken by the principal investigator or a designated covering staff member, in order to supply information required for emergency medical care of research subjects. All subjects will be given a “wallet card” which identifies them as a study participant and lists the emergency contact numbers. If a subject shows clinical deterioration (worsening of depressive symptoms that is higher than 25% of baseline MADRS scores), the participant will exit the study and a study psychiatrist (or APRN) will determine whether a higher level of care (e.g. referral to treating psychiatrist or referral to emergency or inpatient care) is needed.

***Selection:***

Subject eligibility will first be determined via telephone screening and if records are available, by a preliminary medical record review. A waiver of HIPAA authorization and written informed consent will be obtained for a brief initial phone pre-screen (see Appendix 1) and preliminary medical record review. The phone pre-screen and preliminary medical record review will be done to determine obvious exclusions from the study protocol and to prevent subjects from making unnecessary travel for screening. A separate Phone Pre-screen Identification Page (see Appendix 2) will be completed during each telephone pre-screen so the research staff will have the necessary information to access potential participants’ medical records (with the proper verbal assent) and re-contact them for purposes of appointment scheduling. This identification page will be stored in a separate location from the screening form that will only list the subject ID.

***Recruitment:***

Subjects will be recruited by flyers, public advertisements (e.g., print, newspaper, radio, bus, billboards, online postings (including Trialfacts/Rewards for Research online marketing and recruitment service and Craigslist.com), social media (e.g., Facebook, Twitter, Instagram), digital media (e.g., TV, online radio, podcasts), by word of mouth, clinician referral, contact with community service groups and clinics, and through IHR0010, Screening for Depressive, Anxiety, and Trauma and Stress-Related Disorders. We intend to register our study on clinicaltrials.gov. We may also utilize the National Center for PTSD newsletter to advertise the study. Subjects will be identified by their response to advertisements and/or internal recruiting. The subjects will be asked to call us if they are interested in participating in the research study. A waiver of HIPAA authorization and written informed consent will be requested for a phone screen and preliminary medical record review in advance of scheduling the in-office screening procedures. There will not be any web-based questionnaires utilized for pre-screening subjects in this study. All available research staff are responsible for recruiting potential subjects.

[figure not shown]
### **Research Plan and Study Procedures:**

This is a double blind, placebo-controlled, crossover, randomized controlled trial investigating the impact of sirolimus on ketamine's antidepressant effects in participants with antidepressant-resistant depressive symptoms. Participants will be treated twice with ketamine 0.5 mg/kg infused over 40 minutes, combined with a single dose of sirolimus 6 mg orally or placebo. The 2 infusions of ketamine are separated by at least 2 weeks interval because based on previous studies the majority of patients return to their baseline depression severity within this time period. A description of each study visit is provided here and summarized in Figure 3. See Table 1 for detail regarding the schedule of study events.

#### **Day 0-Baseline Screening:**

Individuals deemed eligible after the telephone pre-screening will undergo a full in-person screening appointment at the VA Connecticut Healthcare System (VACHS), West Haven campus. During the evaluation, the study procedures will be described and the subject's questions will be answered prior to obtaining an informed consent. The investigator or research staff member obtaining consent will ask the participant to provide a brief summary of the study to ensure they understand what is being asked of them and any potential risks and benefits. Once consent is obtained, subjects will participate in the following procedures: a biopsychosocial interview, psychological evaluation, a brief cognitive evaluation, a physical examination, ECG, breathalyzer and a blood sample

Figure 3. Phase 2 study design.

for routine testing. A urine sample will be collected for urine toxicology, pregnancy, and urinalysis.

In addition, because this is a clinical trial for medications for increased safety pre-cautions, female subjects of childbearing age will have a blood sample drawn for a pregnancy test. If a female subject is pregnant, breast-feeding, intending to become pregnant, or does not agree to use an approved birth control method (i.e., oral, injectable, or implant birth control, condom, diaphragm with spermicide, intrauterine device, tubal ligation, abstinence, or partner with vasectomy) she will be excluded.

After completing the baseline screening and being deemed eligible for participation in the study, subjects will be randomized to one of two conditions at Time/Infusion 1 — ketamine+sirolimus (with placebo at Time 2) or ketamine+placebo (with sirolimus dose at Time 2).

#### ***Day 1 / Infusion 1:***

First, the MADRS assessment will be completed to confirm that the participant continues to have significant depressive symptoms (i.e. MADRS  $\geq 18$ ) prior to proceeding with Infusion 1. Participants will be rescheduled if depression severity was not met‡. If depression severity is confirmed, Infusion 1 procedures will be completed as follows:

- Subjects will present to the VACHS to complete vitals and provide a urine sample for drug and pregnancy testing.
- Subjects will receive a single 6 mg oral dose of sirolimus or placebo, dependent on their randomization. They will be monitored for any acute allergic reaction or other adverse event. Clinical assessments will be administered throughout the infusion visit, including PSWQ, PSQI, MADRS, QIDS-SR, SAFTEE, CGI, HAM-A, CADSS, PANSS\*\* (assessment measures are described below).
- Intravenous lines will be placed.
- A blood draw for sirolimus level will occur prior to the beginning of the ketamine infusion.
- Ketamine 0.5 mg/kg will be infused over approximately 40 minutes. Subjects will be monitored closely by study physician and nurse.
- A blood draw for ketamine will occur during the ketamine infusion.
- One additional blood draw for sirolimus will occur shortly before the participants are discharged from their study visit.
- Subjects may be discharged home after being cleared by a study physician.

‡ Screening procedures will be repeated if participant was not randomized within 60 days of screening. \*Blood pressure, heart rate, and oxygen saturation will be recorded every 10 minutes during infusion (T0-40 minutes). \*\* Items that could not change within a session, e.g. sleep and appetite, will be carried forward from the initial ratings.

#### ***Day 2+ / 24-hour Follow-Up:***

Subjects will present to the VACHS to complete clinical assessments and a brief cognitive assessment. They will be asked about any residual side effects of other adverse events (AEs) and any appropriate referral for treatment will be made as necessary.

**Days 3-7+/ Phone Follow-Up:**

A study staff member will contact participants by telephone every other day after the 24-hour follow-up until day 7 of the study to track symptom trajectory using QIDS and MADRS. During these telephone follow-ups, subjects will also be asked about potential side effects or interaction effects they may be experiencing related to the study medications.

**Day 8+ / 7-Day Follow-Up:**

The procedures for this visit are identical to those described above for Day 2. For special circumstances (e.g., inclement weather, transportation issues, considerable travel burden, etc.) this visit may occur over the phone. In the cases where a phone visit is required, we will forego the cognitive testing as there is not a way to administer this remotely, but all clinical measures and review of AEs will take place.

**Day 15+ / 14-Day Follow-Up and Infusion 2:**

First, the MADRS assessment will be completed to confirm that the participant continues to have significant depressive symptoms (i.e. within 20% of their baseline MADRS) prior to proceeding with Infusion 2. If depression severity is confirmed, Infusion 2 procedures will be identical to Infusion 1. As this is a crossover study, those subjects who received sirolimus on Day 1 will receive placebo in the second infusion and those who received placebo will receive sirolimus.

Based on several studies, we predict the vast majority of subjects will have returned to within 20% of their baseline depressive symptoms within the 2 weeks period. Should a subject not have returned to within 20% of their baseline depressive symptoms, Infusion 2 will be rescheduled. We will continue to monitor the participant weekly with full assessments identical to Day 2. Participants will be discharged from the study should they maintain these benefits for more than 5 weeks after Infusion 1.

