**III. PURPOSE:**

Ketamine is an anesthetic agent, recently found to exert a rapid and potent antidepressant effect in severely depressed patients. Controversy exists in the field regarding how ketamine works in the brain and thus what underlies its rapid and profound antidepressant effects. A better understanding of the mechanism of the neuropsychiatric effects of ketamine are critically important, as pharmacological modulation of these effects can assist in the development of novel medications for the treatment of multiple psychiatric disorders including depression and schizophrenia.

The aim of the study is to provide insight into the impact of the immunosuppressant drug sirolimus (also known as rapamycin; known to have impact on depressive symptoms from molecular and preclinical studies), on the antidepressant effects of the prototypal rapid-acting antidepressant medication, ketamine. More specifically, the study will examine whether sirolimus shows significant interactive effects (i.e., synergy or antagonism) with ketamine in participants with treatment resistant depression as measured by the use of the clinician-administered Montgomery Asberg Depression Rating Scale (MADRS). We will also test the tolerability of the combined ketamine and sirolimus treatment. Secondary outcome measures are designed to measure the effects of sirolimus on the tolerability of ketamine.

- **Aim 1:** To characterize the effects of a single dose of sirolimus prior to a low dose of ketamine in subjects with antidepressant-resistant depressive symptoms.  
**Design:** 30 participants will be randomized into one of two groups at Time/Infusion 1 — ketamine+sirolimus (with placebo at Time 2) or ketamine+placebo (with sirolimus dose at Time 2).  
**Hypothesis:** Sirolimus will interact with ketamine by attenuating or potentiating the antidepressant effects.
- **Aim 2:** To examine the safety and tolerability of combined ketamine-sirolimus treatment.  
**Design:** The Systematic Assessment for Treatment Emergent Effects (SAFTEE) scale will be completed during each visit to compare the adverse events profile in the sirolimus and the placebo groups.

**Hypothesis:** Participants will tolerate the combined treatment with no residual adverse effects.

- **Aim 3:** To identify biological markers of the combined ketamine-sirolimus treatment.
- **Design:** Inflammatory biomarkers will be measured in 18 depressed participants who will receive open-label sirolimus+ketamine.

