Thus, we have the basis for proposing to test the interactive effects of ketamine and sirolimus, a simple clinical trial that has: 1) the potential to shed fundamental light on how ketamine produces rapid clinical improvement and 2) to suggest a strategy for increasing the effectiveness of ketamine. If sirolimus reduces the antidepressant effects of ketamine, then we will know that stimulation of mTOR is critical to the antidepressant effects of ketamine, leading us to test other drugs that directly stimulate this signaling pathway.

The results of Phase 1 & 2 of this study have shown sirolimus pretreatment significantly prolong the antidepressant effects of ketamine and triples the antidepressant response rate at 2 weeks following treatment (see Fig. 2). Given the role of the immune system in the pathology and treatment of depression, it was proposed that the anti-inflammatory effects of the combined treatment of sirolimus+ketamine underlie the robust enhancement in treatment response rate. Therefore, we will conduct a pilot study to determine the effects of sirolimus+ketamine on a range of inflammatory biomarkers implicated in the pathology of depression. The aim of this Phase 3 of the study is to provide preliminary data about target engagement of the sirolimus+ketamine treatment. The treatment and follow-ups will be comparable to the Phase 2 study, but only open-label sirolimus+ketamine will be administered and the weekly follow-ups will be extended to 4 weeks post-treatment.

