**A. Phase Two Research Procedures (following DSMC approval) Subjects:**

We anticipate recruiting and screening approximately 75 male and female Veterans and non-Veterans/civilians, between the ages of 21-65 years, in order to meet our target enrollment goals. In order to account for subject dropouts and the potential need to discontinue subjects before study completion (see below for discontinuation criteria) and retain a sample of 30 subjects completing the double-blind treatment phase, 45 eligible subjects who meet criteria for Major Depressive Episode as determined by the Mini International Neuropsychiatric Interview (MINI) the study inclusion criteria outlines below, will be randomized into the study. Note, this study will not include a healthy control group as we are interested specifically in the antidepressant effects of ketamine and sirolimus and therefore require subjects with current depression.

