***Data Analysis:***

This study, investigating the impact of sirolimus on ketamine's rapid antidepressant effects, is the first of its kind. In order to assess study utility and to determine if medication dose adjustments may be useful, we plan to do interim analyses after completion of the first 6 subjects, with subjects randomized according to block randomization (block of six). We propose to study 30 patients, overall. This sample size is feasible within the funding available for this project and will provide 80% power for detecting ketamine-sirolimus interaction effects of moderate size ( $d'=.53$ ), assuming a two-tailed alpha=.05. The data analysis plan is provided only for the primary outcome variable, the MADRS score. The normality of the data will be tested initially using probability plots and the Kolmogorov-Smirnov tests. These data are frequently skewed and so we plan to analyze them using a non-parametric approach to repeated measures data. The data will be first ranked and then fitted with a mixed-effects model with an unstructured variance-covariance matrix and p values adjusted for ANOVA-type statistics. In these models sirolimus (active vs. placebo) and time will be fitted as within subjects variables. All interactions will be fitted. Age and sex will be treated as covariates/grouping factors. Post-hoc analyses will be conducted to interpret interactive effects significant at the p=0.05 level. Subject will be used as the clustering variable. Plasma ketamine and ketamine metabolite levels will be analyzed using linear mixed models. All secondary measures will be assessed using similar methodology. Behavioral measures of Phase 3 will use similar methodology. The collection, processing and analysis of peripheral inflammatory biomarkers will be completed under a separate protocol and consent (i.e., CA0008).

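### The crossover model names no period term or analysis set although entry to Period 2 depends on the Period 1 outcome, and the number randomised is given as both 30 and 45

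*Combined protocol and SAP*

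**What the plan says.** All places are in the combined protocol and SAP.

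- **Entry to Period 2** (Day 15+ / 14-Day Follow-Up and Infusion 2). MADRS must be within 20% of baseline before Infusion 2; otherwise the infusion is rescheduled. In the meantime, "We will continue to monitor the participant weekly with full assessments identical to Day 2". The endpoint of that wait is: "Participants will be discharged from the study should they maintain these benefits for more than 5 weeks after Infusion 1". The same section predicts that nearly all participants will be back in range by two weeks.
- **Model** (Data Analysis). A mixed-effects model on ranked MADRS with unstructured covariance, clustered on subject: "In these models sirolimus (active vs. placebo) and time will be fitted as within subjects variables". All interactions are fitted, and age and sex are the only other terms named. Period and sequence are not mentioned, and no analysis set is defined.
- **Power** (Data Analysis). "We propose to study 30 patients, overall"; this number "will provide 80% power for detecting ketamine-sirolimus interaction effects of moderate size", with d' = 0.53 and two-tailed alpha 0.05. The standard deviation behind d' is not stated.
- **Number randomised.** Purpose, Aim 1: "30 participants will be randomized into one of two groups at Time/Infusion 1". Phase Two, Subjects: dropouts and discontinuations are allowed for, so that to "retain a sample of 30 subjects completing the double-blind treatment phase, 45 eligible subjects" will be randomised.
- **Who crosses over.** The Ketamine Administration section after the Phase Three text has every participant receiving two infusions. The phone pre-screen script in Appendix 1 expects this only of most.

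**The concern.** In a two-period crossover each participant's treatment difference is also a period difference, with its sign set by sequence. A period term separates the two. Without it, a general shift between periods sits in the residual of the treatment comparison, and it stops averaging out once the sequences are unequal.

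This plan has a mechanism that can make them unequal. Participants with the most durable Period 1 benefit supply no Period 2 data. If sirolimus prolongs benefit, more of them come from the sirolimus-first sequence. The Background reports that sirolimus pretreatment prolongs ketamine's effect and "triples the antidepressant response rate at 2 weeks following treatment", and Phase Three follow-up was lengthened for that reason. An analysis restricted to those who crossed over would lose these participants, which pulls the estimated effect toward zero.

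The sample-size text raises a separate question. If 30 means 30 randomised, each participant without a second period takes power below the stated 80%. If it means 30 completing, the figure stands.

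**Working it through.** **1. The plan's own power figure.** Inputs from Data Analysis: n = 30, d' = 0.53, two-sided alpha 0.05. For a paired t-test with d' standardised by the SD of the within-subject difference, the noncentrality is d'√n and the degrees of freedom are n − 1.

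- n = 30: 0.53 × √30 = 2.903, critical t(29) = 2.045, power **80.1%**.
- n = 29: 0.53 × √29 = 2.854, critical t(28) = 2.048, power **78.7%**.
- n = 27: 75.5%. n = 24: 70.1%.
- Two independent groups at the same d': 15 per group 28.9%, 30 per group 52.3%.

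Of the readings tried with a two-sided t-test, only 30 complete pairs reproduces 80%. The Phase Two section supplies exactly that: 30/45 = 66.7% retained, an allowance of 33.3%. Aim 1's 30 randomised supplies it only if nobody is lost.

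**2. Power cost of a period term.** The treatment estimate is the mean of the two sequence means. In units of the SD of the within-subject difference its standard error is ½√(1/n₁ + 1/n₂), with n − 2 = 28 degrees of freedom.

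- 15/15: SE 0.1826, noncentrality 0.53/0.1826 = 2.903, power **80.0%**, a cost of 0.1 points.
- 17/13: SE 0.1842, noncentrality 2.877, power **79.3%**, a cost of 0.8 points.

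**3. What omitting period does to a level contrast.** Let τ be the sirolimus effect and π the Period 2 minus Period 1 shift, both in the same SD units. A sirolimus-first participant's sirolimus-minus-placebo difference has mean τ − π; a placebo-first participant's has mean τ + π. The documents give no π, so 0.1 to 0.5 is an assumed range.

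*Balanced, 15/15.* The estimate is still τ, but the sample variance of the differences rises from 1 to 1 + π² × 30/29.

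| π | SE without period | power without period |
|---|---|---|
| 0 | √(1/30) = 0.183 | 80.1% |
| 0.1 | √(1.0103/30) = 0.184 | 79.8% |
| 0.25 | √(1.0647/30) = 0.188 | 78.3% |
| 0.5 | √(1.2586/30) = 0.205 | about 73% |

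The power entries for π > 0 come from simulation of this paired test (400,000 draws). With the period term, power stays at about 80% throughout.

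*Unequal, assumed 13 sirolimus-first and 17 placebo-first pairs.* The estimate becomes τ + π(17 − 13)/30 = τ + 0.133π. For π of 0.1, 0.25 and 0.5 it moves by 0.013, 0.033 and 0.067, which is 2.5%, 6.3% and 12.6% of 0.53. The direction follows the sign of π.

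**4. Treatment-by-time contrast.** MADRS is taken before each infusion. If Period 2 raises or lowers every visit by π, then (post + π) − (pre + π) = post − pre, so the shift drops out. This is exact on raw scores and approximate on ranks. It fails if the shift varies over visits.

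**5. Period 1-only participants: direction of effect.** An illustrative simulation used 30 participants, within-subject correlation 0.5, one outcome per period and known covariance. Period 2 was missing when the Period 1 outcome exceeded 1.0 to 1.5 SD, and each setting had 1,500 runs. For a true effect of 0.53:

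- Complete pairs without a period term: bias −0.04 with no period shift, −0.06 to −0.09 with a shift of −0.5.
- Mixed model keeping Period 1-only participants, without a period term: about 0 with no shift, −0.02 to −0.04 with a shift of −0.5.
- The same model with a period term: within 0.01 of zero in all settings.
- True effect 0: every estimator within 0.01 of zero.

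These values show direction only. The documents give no discharge rate from which to set the gate.

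**The case against.** The best defence is that a mixed model clustered on subject, fitted by likelihood, keeps participants with one period by default. Because the gate acts on recorded MADRS, the missingness is compatible with missing at random when those scores are in the model. Block randomisation in sixes starts the sequences near balance. The reported Phase 2 finding (figure legend under Significance) is a treatment-by-time interaction, where a constant shift largely cancels. The Phase Two section already randomises enough for 30 completers. All of this stands, and it limits the point to an unstated term, an unstated analysis set and inconsistent wording.

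A reader might go further in three ways that the documents do not support.

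- *That the plan drops sustained responders and so biases the result.* No section calls for a completers-only analysis. The text is silent, which permits one but does not prescribe it. How much it would attenuate the effect cannot be worked out from the documents. The prediction of near-complete return by two weeks points to a small amount, and the reported prolongation to a larger one.
- *That the reported Phase 2 benefit could be an artefact.* No estimator produced an effect under the null, and attenuation works against a benefit.
- *That the trial is underpowered.* This follows only if the Aim 1 summary line overrides the detailed Phase Two text.

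It could also be argued that time, if coded over all study days, absorbs period. The section crosses time with sirolimus as within-subject factors and does not say this.

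**Conclusion.** The point holds in limited form, at minor to moderate severity.

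The model omits a standard crossover term in a design whose own rules can unbalance the sequences. The consequence is lost precision on a level contrast: up to about 7 points of power if the period shift is as large as 0.5 SD, and under 2 points at 0.25 SD or less. The same contrast can also move slightly if the sequences end unequal; the movement is appreciable only if imbalance and shift are both large. Both statements rest on assumed shifts, an assumed 17/13 split and a complete-pair t-test standing in for the planned rank model.

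The sample-size point needs one assumption, that d' is standardised by the SD of the within-subject difference. On that reading the 80% is correct for 30 complete pairs and agrees with the Phase Two section; the Aim 1 line is the one out of step. It remains unclear whether the allowance of 15 covers sustained responders, because the reasons listed under Criteria for Discontinuation do not include them.

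**What to change.** 1. Add period as a fixed effect to the model in Data Analysis.
2. State that all randomised participants who received the Infusion 1 study drug are analysed by likelihood, including those with Period 1 data only. Give completers as a sensitivity analysis.
3. Use the scheduled visits common to both periods in the unstructured model. The week 3 to 5 gate visits exist only for participants who had not returned to range, and whether an unstructured model of this size can carry them has not been shown. Use them descriptively or in a sensitivity analysis. That sensitivity analysis matters, because late discharge decisions rest on those scores.
4. Report by sequence the number who did not cross over.
5. Change Aim 1 and Data Analysis to 45 randomised with 30 completing both periods, and state that d' uses the SD of the within-subject difference. Say whether the allowance of 15 includes sustained responders.
6. Reconcile the Ketamine Administration wording that all participants receive two infusions with the Infusion 2 section, leaving every clinical rule as it is.

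Phase 2 results are already reported, so any application to those data should be labelled a post-hoc sensitivity analysis. The power cost of the period term is 0.1 points at 15/15 and 0.8 at 17/13. The rest is one table, one or two sensitivity fits and wording; no new data are needed.
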